Feasibility Study to Improve Atrial Fibrillation Outcomes Using a Digital Application for Cardiovascular Risk Reduction: Precursor to a Multicenter Randomized Trial

Study Protocol and Statistical Analysis Plan

NCT04050982

May 17, 2022

Title Feasibility Study to Improve Atrial Fibrillation Outcomes using a Digital Application for Cardiovascular Risk Reduction: Precursor to a Multicenter Randomized Trial

Purpose

An effective intervention to support cardiovascular risk factor (CVRF) reduction in individuals with AF that can be easily provided with existing resources does not exist, despite the evidence that even though CVRF reduction has been shown to decrease AF symptom severity and burden. The digital application, AF CARE, has been specifically designed to fill this critical need to support CVRF reduction in individuals with AF, and can be easily incorporated into the care delivered to individuals undergoing AF catheter ablation (CA), but its feasibility is unknown. Demonstrating that an available digital application can improve AF outcomes would be significantly impactful.

The specific aims of this study are to: 1). Test the feasibility of AF CARE in terms of acceptability, demand, usage, adherence, and integration (1), and 2). Determine the efficacy of AF CARE based on the pre-post assessment of CVRF (LS7 and/or blood tests), AF knowledge, AF Symptom Severity and Burden (AFSS), and QOL assessment at baseline, 3, and 6 months in the AF CARE group compared to the usual care (UC) group to provide estimates of effect size.

Background and Significance

Atrial fibrillation (AF) is the most common cardiac arrhythmia disorder in the United States, contributing to a five-time greater risk of stroke and is independently associated with increased mortality (2,3). Predictions of doubling the AF population is based on aging and increased prevalence of cardiovascular risk factors (4). A predicted lifetime risk of AF rises from 20% to 33% with the addition of a single elevated CVRF (4,5,6). Innovative interventions that promote the reduction of CVRF are needed to decrease AF symptom severity and burden.

Current AF treatment guidelines include CVRF reduction, and when reduced in a randomized group, particularly weight loss, there was a significant reduction in AF burden and AF symptoms compared to those who received usual care (7,8). A maintained weight loss of at least 10% contributed to the greatest reduction in AF symptoms and AF burden (9). While AF CA procedures significantly reduce AF symptom burden (10) and decrease AF associated mortality and morbidity (11), recurrences resulting in increased morbidity and mortality persist (12). Altering the disease substrate with CVRF reduction and modifying the electrical substrate with CA procedures has shown an improvement in post-AF ablation outcomes, with less AF symptom severity/burden (13,14).

Lifestyle modifications to reduce CVRFs are difficult. There is no consensus on which intervention for CVRF reduction is most effective (15), nor what delivery mode is most acceptable. The American Heart Association (AHA) Center for Health Technology and Innovation collaborated with the Stanford Center for Digital Health and PatientBond, a digital technology software company, to design a personalized digital application (app) that can be accessed via a smartphone, iPad, or personal computer (16). This digital app, AF CARE, delivers patient-specific messages to promote behaviors that will reduce

CVRF and improve AF knowledge, based on each individual's responses to 12 psychographic questions, 12 AHA Life's Simple 7 (LS7) questions, and specific biometrics. To date, the utility and effectiveness of AF CARE to reduce CVRF has not been tested.

Research Design

Phase I will be completed prior to randomization on 10 individuals with AF who will be asked to participate in interface testing of the digital platform for 1-3 months to identify potential programming modifications to enhance usage and adherence.

Then, the primary aim of Phase II of this study will be to determine feasibility of utilizing AF CARE to provide lifestyle modification support to patients with AF. The secondary outcome will be to compare the CVRF, AF knowledge, AF Symptom Severity and Burden, and QOL between and within the UC group and the CARE AF group. This feasibility study will use a prospective, RCT wait list design to allow for the determination of effect sizes to inform the power calculation for a multi-center trial, if found to be effective. (Phase I).

a. Sample: Sixty patients undergoing treatment for AF at Stanford Health Care.

Inclusion: ≥ 18 years old, $\text{BMI} \geq 28 \text{ kg/m}^2$ AND one additional CVRF, access and willingness to engage in digital technology, has a valid email address and a cell phone number, and able to ambulate and speak/read English

Exclusion: Class III/IV heart failure, MI or cardiac surgery in prior 3 months, severe renal/hepatic disease, active malignancy, current/recent (within 6 months) enrollment in weight loss program.

b. Participants will be recruited when they are being followed for the management of their atrial fibrillation in the Stanford clinic.

c. Procedure: Individuals meeting inclusion criteria, but not excluded, will be invited to participate. Once consented, demographics, biometrics and baseline measures will be collected. Both groups will be asked to enter initial responses into AF CARE and then will be randomized to either the digital platform AF CARE group and UC or Wait List Group. The UC wait list group will receive usual care for the first 3 months and then they will receive the digital platform (AF CARE) after 3 months of enrollment. Both groups will be appropriately referred for smoking cessation, behavioral medicine, endocrinology, and/or sleep clinic during initial and Month 3 visit, based on screening completed at that visit. Initial measures will be collected, and repeated at Month 3, Month 6, and Month 12.

Both AF CARE/UC and Wait List Groups	Initial	Month 3 (CA)	Month 6	Month 12
Medical History and Physical	X	X	X	X
Demographics	X			
Psychographic score	X			
AHA Life's Simple 7	X	X	X	X
Biometrics- pt reported (BP, HR, RR, waist, BMI)	X	X	X	X
Blood testing, if available: Lipid panel, Blood Sugar	X		X	X
6 Minute Walk Test	X	X	X	X
Jessa AF Knowledge Questionnaire	X	X	X	X
AF Symptom Severity Scale (AFSS)	X	X	X	X

Ambulatory Monitor (Zio patch)- if available	X	X	X	X
AF Effect on Quality of Life (AFEQT)	X	X	X	X
AF CARE Group -Access to AF CARE	X-----→			
Wait List Access to AF CARE	X-----→			

AF CARE GROUP: Patients will receive personalized messages twice weekly that will include behavior recommendations for CVRF reduction and AF education from the AHA library. Messages will be patient-specific based on the initially entered psychographic profile and data entered.

Ongoing messages will include participant response requests and future messages elicited by AF CARE will be based on entered responses.

During the protocol, 3 participant non-responses to communications will result in a message being sent to the research team to prompt a call to the participant to enforce the importance of the messaging. In addition, a participant posting a negative response (e.g. "I do not know how to get my medicine refilled") will also result in a message being sent to the research team to determine if clinical follow-up is required.

Wait List UC Group/AF CARE Group: Participants will be given a weight loss goal of 10% and other recommendations for CVRF reduction based on their initial LS7 assessment. They will be provided written educational materials to review independently on AF and AF CA treatment.

Participants in this group will receive personalized messages twice weekly that will include behavior recommendations for CVRF reduction and AF education from the AHA library starting at 3 months following randomization. Measurable Outcomes: (See Table above).

- a. CVRF will be evaluated using the pre-post measures of the AHA Life's Simple 7, along with patient reported blood pressure, BMI, blood tests (lipids and glucose), and 6-minute walk test.
- b. AF knowledge will be evaluated with the Jessa AF Knowledge Questionnaire
- c. AF Symptom Severity and Burden will be measured with the AF Symptom Severity Scale
- d. QOL will be measured with the AF Effect on Quality of Life Questionnaire, and the Patient Health Questionnaire-9

Data Analysis: Demographic data will be analyzed using descriptive statistics for continuous data and frequencies and percentages for categorical data.

The feasibility of AF CARE will be determined by calculating acceptability, demand, AF CARE usage, adherence, and qualitative interview data analysis.

Efficacy will be evaluated on CVRF, AF Knowledge, AF symptom severity and burden, and QOL using matched pair t-tests at baseline, 3 and 6, and 15 months to determine the differences between and within groups. This data will be used to calculate the sample size required in a future multicenter trial designed to achieve 80% power to detect a change of 10% from baseline.

- d. Potential Pitfalls: Data integrity is an issue for self-reported measures in the usual care group. The level of usage with the AF CARE plan may be suboptimal or AF CARE may be ineffective in meeting study aims.

e. Sustainability: Sustainability will be determined by participant engagement and efficacy.

References

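### Aim 2 names a 6-month AF CARE versus usual care effect size, but the usual care arm starts AF CARE at Month 3, so only Month 3 gives that contrast

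*Combined protocol and SAP*

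**What the plan says.** Specific aim 2 (Purpose) calls for pre-post assessment of risk factors, AF knowledge, symptoms and quality of life "at baseline, 3, and 6 months in the AF CARE group compared to the usual care (UC) group to provide estimates of effect size". Research Design describes a wait-list randomised trial whose effect sizes will inform the power calculation of a multicenter trial. It plans comparisons "between and within the UC group and the CARE AF group".

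Two places fix when the control arm crosses over. Research Design, c. Procedure: "The UC wait list group will receive usual care for the first 3 months and then they will receive the digital platform (AF CARE". The paragraph headed Wait List UC Group/AF CARE Group says this arm receives personalised messages with "AF education from the AHA library starting at 3 months following randomization".

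Visits are set at the initial assessment and Months 3, 6 and 12. Data Analysis evaluates efficacy "using matched pair t-tests at baseline, 3 and 6, and 15 months to determine the differences between and within groups". It does not say which contrast is made at which visit. Nothing in the document limits the usual care contrast to Month 3 or gives the later between-arm differences another name.

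**The concern.** Aim 2 ties the 6-month time point to a usual care comparator and to an effect size. By Month 6 the comparator has had 3 months of the same app. An analyst following Aim 2 as written would report an immediate-versus-delayed difference as an AF CARE versus usual care effect. An app that does all its work within 3 months could then show no difference at Month 6 and be read as ineffective.

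Supplying planning values for the multicenter trial is a stated purpose of the design, so a mislabelled effect size could be carried forward. How far is unclear, because Data Analysis sizes the future trial on a 10% change from baseline.

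The within-arm summaries have a related problem. For wait-list participants, change from the initial visit to Month 6 combines 3 months of usual care with 3 months of AF CARE.

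**Working it through.** **Inputs.** Comparison at 3 and 6 months (Purpose, aim 2); wait-list access from Month 3 (c. Procedure and the wait-list paragraph); visits at Months 3, 6 and 12 (c. Procedure). The plan has no figure to reproduce here: the sample of 60 has no derivation, and the 80% power belongs to the future trial, with no SD or alpha.

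**Step 1: exposure.** At visit *m*, the AF CARE arm has had *m* months of the app and the wait-list arm max(0, *m* − 3).

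| Visit | AF CARE arm | Wait-list arm | What the difference estimates |
|---|---|---|---|
| Month 3 | 3 | 3 − 3 = 0 | AF CARE versus usual care |
| Month 6 | 6 | 6 − 3 = 3 | Immediate versus delayed access |

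Month 12 is the same kind of contrast as Month 6 if access continues. The prose does not say how long access lasts, and the span of the access arrows in the schedule table cannot be read from the extracted text.

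**Step 2: what Month 6 measures.** Let f(6) be the effect of 6 months of AF CARE versus usual care. Let g(3) be what the wait-list arm has gained by Month 6 from its own 3 months. The between-arm difference is D6 = f(6) − g(3), so the share of the 6-month effect that it shows is D6/f(6) = 1 − g(3)/f(6).

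| g(3)/f(6) | Share shown at Month 6 |
|---|---|
| 0 | 100% |
| 0.25 | 75% |
| 0.50 | 50% |
| 0.75 | 25% |
| 1.00 | 0% |
| 1.25 | −25% (sign reversed) |

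**Step 3: if start time does not matter** (assumption, g(3) = f(3)).
- Linear build-up, f(t) = kt: D6 = 6k − 3k = 3k, and 3k/6k = 50%.
- Effect complete by Month 3 and persisting, f(3) = f(6): D6 = 0.
- No effect before Month 3, f(3) = 0: 100%.
- Waning, for example f(3) = 0.4 SD and f(6) = 0.2 SD: D6 = 0.2 − 0.4 = −0.2 SD.

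**Step 4: if start time matters.** The Month 3 column of the schedule carries the letters CA without explanation, and the Purpose section uses CA for catheter ablation ("individuals undergoing AF catheter ablation (CA"). Starting the app at Month 3 may therefore not be equivalent to starting at enrolment. Take assumed values f(6) = 0.4 SD and f(3) = 0.2 SD, and let g(3) be 50% smaller than, equal to, or 50% larger than f(3):
- g(3) = 0.1: D6 = 0.3 SD, 0.3/0.4 = 75%.
- g(3) = 0.2: D6 = 0.2 SD, 50%.
- g(3) = 0.3: D6 = 0.1 SD, 25%.

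**Step 5: effect on future planning (illustration only).** The required sample size varies as 1/effect², so planning on D6 instead of f(6) multiplies it by 1/(1 − r)², where r = g(3)/f(6). For r = 0.25, 0.50 and 0.75 the factors are 1.78, 4 and 16. Assume a true effect of 0.5 SD, two-sided alpha 0.05 and 80% power. Then 63 per arm becomes 112, 252 or 1005. None of these inputs comes from the documents except the 80% power.

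**Step 6: blood tests.** Aim 2 defines the risk-factor outcome as "CVRF (LS7 and/or blood tests"). In the schedule as extracted, the row "Blood testing, if available: Lipid panel, Blood Sugar" has no Month 3 entry, although c. Procedure repeats the initial measures at Month 3. On the table's reading, lipids and glucose have no AF CARE versus usual care contrast after baseline. The other risk-factor measures (LS7, blood pressure, BMI, walk test) keep theirs.

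**The case against.** The strongest reply is that Aim 2 lists assessment times and does not specify a Month 6 between-arm test. In an openly declared wait-list design, a reader would naturally take the between-arm contrast during the wait and within-arm change afterwards. On that view the plan leaves a contrast unspecified and does not commit to a wrong one. Data Analysis is indeed silent on which contrast belongs to which visit. But Aim 2 itself joins the 6-month point to the usual care comparison and to effect size, and no other text corrects it. The natural reading has to be supplied by the reader.

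A second objection is that the magnitude is unknown. The share runs from 100% through 0% to reversed sign, and every illustrative input is assumed. That stands: the calculation shows that Month 6 cannot be read as the usual care effect, not how far off it would be.

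Third, this is a secondary aim in a 60-person feasibility study, and the future trial is to be sized on a 10% change from baseline. That also stands and limits the severity.

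Finally, paired t-tests do not suit a comparison of two independent arms, so rewording alone does not give a usable between-arm analysis. That is correct, but it is a separate defect.

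**Conclusion.** The concern holds. The 6-month AF CARE versus usual care effect size named in Aim 2 cannot be obtained from this design as a between-arm difference, because the control arm has had 3 months of AF CARE by then. This follows from two separate prose statements of the crossover time and does not depend on the schedule table. Month 3 is the only scheduled post-baseline AF CARE versus usual care contrast. It requires Month 3 measures to be taken before wait-list access opens, which the text implies but does not state. The comparator there is usual care as the protocol describes it, including a weight-loss goal and written materials.

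The Month 6 difference remains a valid randomised estimate of immediate versus delayed access. Its relation to the 6-month effect depends on the unknown rate of build-up and on whether start time matters. Feasibility, the primary aim, and the Month 3 contrast are not affected by the crossover. This should be fixed, because the effect sizes are meant to inform a larger trial and the correction costs little.

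**What to change.** Amend Aim 2 and Data Analysis as follows.

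1. Define the AF CARE versus usual care effect size as the Month 3 between-group difference, measured before wait-list access opens, and describe it as a 3-month effect.
2. Label between-arm differences at Month 6 and later *immediate versus delayed AF CARE*. Do not use them as AF CARE versus usual care effect sizes; they can still answer a question about timing of access.
3. Use Month 3 as the pre-app baseline in wait-list pre-post summaries.
4. Reconcile the Month 3 blood-test cell with the text that repeats initial measures at Month 3. Make no AF CARE versus usual care claim for lipids or glucose unless Month 3 values exist.

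Two separate points can be settled in the same edit: replace the paired test with an independent-groups analysis for between-arm differences, and reconcile the 15-month analysis with a visit schedule that ends at Month 12.

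The cost is mostly wording plus one procedural rule on the order of Month 3 measurement and wait-list access. No visits or participants are added. The downside is that the randomised AF CARE versus usual care effect covers only 3 months of app use, a limit the design already imposes.

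### The role of catheter ablation (CA) is inconsistent: the rationale points to the CA pathway, any AF clinic patient can enrol, and planned or performed CA is neither itemised nor used in randomisation or analysis.

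*Combined protocol and SAP*

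**What the plan says.** Some parts of the plan point to CA patients:

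- The Purpose says the app "can be easily incorporated into the care delivered to individuals undergoing AF catheter ablation (CA), but its feasibility is unknown".
- In the schedule under c. Procedure, the Month 3 column carries the tag (CA) for both arms. The tag is not explained.
- The wait-list group receives "written educational materials to review independently on AF and AF CA treatment".

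Other parts cover AF patients in general:

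- The Purpose also says the app "has been specifically designed to fill this critical need to support CVRF reduction in individuals with AF".
- The Phase II primary aim in Research Design is to "determine feasibility of utilizing AF CARE to provide lifestyle modification support to patients with AF".
- Under a. Sample: "Sixty patients undergoing treatment for AF at Stanford Health Care".
- Under b.: "Participants will be recruited when they are being followed for the management of their atrial fibrillation in the Stanford clinic".
- The inclusion and exclusion criteria do not mention CA.

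On handling, participants "will be randomized to either the digital platform AF CARE group and UC or Wait List Group". No allocation ratio, stratification or blocking is given. Data Analysis names matched-pair t-tests with no covariate. The schedule has "Medical History and Physical" at all four visits but no named item for planned CA, performed CA or its date. Background and Significance says that CA procedures significantly reduce AF symptom burden, which is a study outcome.

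**The concern.** Two teams following this text could enrol different mixes of patients: CA planned, CA already done, CA during follow-up, or no CA at all. Two things depend on that mix.

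The first is the feasibility result. Aim 1 includes integration, and the Purpose cites CA care as a setting where the app would fit. If CA status is not identified, nobody can say how many of the sixty speak to that setting or how the app performed there.

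The second is the effect-size estimate that is to inform the multicenter trial. By the plan's own account CA acts on AF symptoms. AFSS measures these directly, and AFEQT may plausibly move with them. A known prognostic factor left out of both randomisation and analysis adds noise to a small comparison. Month 3 matters most, because it is the last visit before the wait list receives the app.

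**Working it through.** **The plan's own figure.** The sample size of sixty has no derivation, so there is nothing to reproduce. The 80% power and 10% change in Data Analysis refer to the future trial.

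**Inputs.** From the plan: N = 60 and two groups. Assumed, because the plan is silent: 1:1 allocation (30 per arm), CA share p of 20% to 70%, CA effect e of 0.5 to 1.0 SD on a symptom outcome, and CA taking place before the measure in question.

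**Step 1: how far the arms may differ in CA by chance.** With independent binomials, the SD of the difference in CA share is sqrt(2p(1−p)/30). The exact chance of a difference of at least 20 points (6 of 30) follows from two Binomial(30, p) counts. With the CA total among the sixty held fixed, it follows from the hypergeometric distribution.

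| CA share | SD of difference | P(≥ 20 points), binomial | P(≥ 20 points), fixed total |
|---|---|---|---|
| 20% | 10.3 points | 0.075 | 0.104 |
| 30% | 11.8 points | 0.120 | 0.158 |
| 50% | 12.9 points | 0.155 | 0.196 |
| 70% | 11.8 points | 0.120 | 0.158 |

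The two models have nearly the same spread. At p = 0.5 the fixed-total SD is 2 × sqrt(30 × 0.25 × 30/59)/30 = 0.130, against 0.129. The tails differ because, with an even fixed total, the difference in counts moves in steps of two.

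**Step 2: what a 20-point difference does to the contrast.** Shift = 0.20 × e. The standard error of a difference in means is sqrt(2/30) = 0.258 SD.

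- e = 0.5: shift 0.10 SD, 39% of the standard error
- e = 0.8: shift 0.16 SD, 62%
- e = 1.0: shift 0.20 SD, 77%

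Even the largest of these is below one standard error.

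**Step 3: the precision lost.** If CA is ignored, the outcome variance is 1 + p(1−p)e², and CA accounts for p(1−p)e²/(1 + p(1−p)e²) of it.

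- p = 0.5, e = 0.5: variance 1.0625, CA share of variance 6%, standard error larger by a factor of sqrt(1.0625) = 1.03
- p = 0.5, e = 1.0: variance 1.25, share 20%, factor 1.12
- p = 0.2, e = 0.5: variance 1.04, share 4%, factor 1.02
- p = 0.2, e = 1.0: variance 1.16, share 14%, factor 1.08

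**Step 4: precision for feasibility in the CA setting.** For a proportion near 50%, the 95% half-width is 1.96 × sqrt(0.25/m), where m is the number of CA patients. For 30%, 50% and 70% of sixty (m = 18, 30, 42) it is 23, 18 and 15 points. For all sixty it is 13 points.

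**Step 5: which visits are affected.** The plan does not say what the (CA) tag means. If CA comes before the Month 3 measures, steps 2 and 3 apply to Month 3. If CA comes at or after that visit, they apply from Month 6 onward, when both arms already have the app and the contrast is early against delayed start.

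**The case against.** The strongest reply is that the plan agrees with itself where it counts. The numbered aims do not mention CA, and the Phase II primary aim, the sample, eligibility and recruitment all describe patients with AF. The clause on unknown feasibility in the Purpose can be read as covering the app as a whole. This stands. A reader might infer that the trial is meant for CA patients and enrols the wrong population. The documents do not support that. They support only an unresolved inconsistency about the role of CA.

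A reader might also infer that CA goes unrecorded. That is too strong as well: the history and physical at each visit could capture it. What is missing is a named item for CA planned, CA done and its date.

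Finally, a reader might infer that the Month 3 comparison is biased. Chance imbalance after randomisation is not bias on average, and the standard error already allows for it. Month 3 is touched only if CA precedes its measures, which the undefined tag leaves open. The documents also give no CA effect on Life's Simple 7, AF knowledge or walking distance, so the calculation should not be carried over to those outcomes.

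These replies limit the point but do not remove it. The tag is still undefined, CA status is not identified, and a prognostic factor named in the plan's own background is not used.

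**Conclusion.** The point holds as an inconsistency to reconcile and a cheap gain in precision. Feasibility in the CA setting would rest on a subgroup of unknown size, and the AFSS and AFEQT contrasts carry avoidable variance at the visits that follow CA. The size is modest: about a 7% to 16% chance (10% to 20% with a fixed total) of a 20-point difference in CA between arms, a resulting shift of 0.10 to 0.20 SD, and a standard error about 2% to 12% larger across the combinations worked above. These figures rest on assumed 1:1 allocation, CA share, CA effect and CA timing, none of which the documents give. The inconsistency itself needs no assumption. Neither the primary aim nor the validity of the randomised comparison is undermined.

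**What to change.** - Record planned CA (yes/no) before randomisation, and the CA date if it is done.
- Stratify the randomisation of the sixty by planned CA, in small blocks.
- Include planned CA as a covariate in the between-arm comparisons of AFSS and AFEQT. This needs a regression model, since a paired t-test cannot hold a covariate.
- Report the feasibility measures by planned CA, descriptively.
- Define the (CA) tag on Month 3, and reconcile it and the Purpose with recruitment: state the population as AF clinic patients, and limit any CA-pathway claim to the planned-CA stratum.

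The cost is one baseline field and a date, a slightly more complex randomisation list, one covariate and some rewording. The strata will be small (about 15 per arm at an assumed 50% share), so their results are descriptive. Stratification balances planned CA, not CA actually performed, so the gain depends on how well the plan predicts the procedure. Marking measures taken after CA is useful description but does not restore balance.

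### The wait-list arm is on AF CARE from Month 3, yet the plan gives it no pre-app baseline and calls it usual care at 6 months, so neither its 6-month change nor the Month 6 between-arm difference is a valid app effect size

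*Combined protocol and SAP*

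**What the plan says.** - **App start.** Procedure (Research Design, item c): "The UC wait list group will receive usual care for the first 3 months and then they will receive the digital platform (AF CARE" app. The wait-list group paragraph agrees: messages and "AF education from the AHA library starting at 3 months following randomization".
- **Baseline.** "Once consented, demographics, biometrics and baseline measures will be collected"; randomization follows. No second baseline is defined for the wait-list arm.
- **Visits.** "Initial measures will be collected, and repeated at Month 3, Month 6, and Month 12", in one table for both arms.
- **Tests.** Data Analysis evaluates efficacy "using matched pair t-tests at baseline, 3 and 6, and 15 months to determine the differences between and within groups". It does not say which visits form a pair in which arm. Research Design plans the secondary comparison "between and within the UC group and the CARE AF group".
- **Role of the wait-list arm.** Specific aim 2 (Purpose) sets out "QOL assessment at baseline, 3, and 6 months in the AF CARE group compared to the usual care (UC) group to provide estimates of effect" (that is, effect sizes).
- **Use of the results.** Research Design says the effect sizes will inform the power calculation of a multicenter trial. Data Analysis says the data will be used to size that trial at 80% power for a 10% change from baseline.

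**The concern.** A wait-list design gives two clean pieces of information. One is a randomized app versus no-app contrast while the controls wait. The other is a before-and-after comparison in the controls anchored at their own app start. The plan isolates neither. With one baseline and one set of time points for both arms, the wait-list Month 6 result spans app-free and app months. The aim 2 comparison at 6 months is worded as AF CARE versus usual care, although the comparator has by then had the app for 3 months.

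What is at stake is the effect size carried into the multicenter trial. A wait-list change that includes usual-care improvement would make that trial too small. A Month 6 between-arm difference shrunk by the controls' own app use would make it too large, or make a useful app look ineffective.

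**Working it through.** **The plan's own figure.** The sample size is 60. No alpha, SD, effect size, allocation ratio or dropout is given for it, so it cannot be reproduced. Below, 30 per arm (1:1) and two-sided 5% tests are assumptions.

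**Months on app since the Initial visit**

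| Visit | AF CARE arm | Wait-list arm | Between-arm comparison |
|---|---|---|---|
| Month 3 | 3 | 0 | app versus no app |
| Month 6 | 6 | 3 | earlier versus later start |
| Month 12 | 12 | 9 | earlier versus later start |

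Only Month 3 compares app with no app. From Initial to Month 6, 3 of the wait-list arm's 6 months (50%) are app-free.

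**Wait-list change from Initial to Month 6.** Let u be the change over months 0 to 3 and a the change over months 3 to 6. A pair formed from these two visits estimates u + a, so as an estimate of the app-period change its bias is u. The documents do not give u. It need not be zero, because this arm receives a weight-loss goal, recommendations based on its LS7 answers, written material and referrals.

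*Chance of p<0.05 when a = 0* (n = 30, Initial-to-Month 6 correlation 0.6, both assumed):
- SD of change = sqrt(2(1 − 0.6)) = 0.894.
- Noncentrality = u / (0.894/√30) = 0.61, 1.22 and 1.84 for u = 0.1, 0.2 and 0.3 SD.
- The noncentral t distribution with 29 df gives 9%, 22% and 43%. At u = 0.3 the range is 36% to 54% for correlations 0.5 to 0.7.

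*Effect on the future trial, if u + a were used as its effect size.* Assume a = 10 points and 80% power; n per arm = 2((1.96 + 0.84)·SD/Δ)², rounded up.

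| SD | n at Δ = 10 | n at Δ = 12 (u = 2) | n at Δ = 15 (u = 5) |
|---|---|---|---|
| 15 | 36 | 25 | 16 |
| 20 | 63 | 44 | 28 |
| 25 | 99 | 69 | 44 |

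With u = 2 the change is overstated by 20%, and power against the true 10 points is about 65%. With u = 5 it is overstated by 50%, and power is 46% to 47%.

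**Between-arm difference at Month 6.** Assume a 6-month app effect of 10 points, of which a fraction f is reached after 3 months on app, the same course after app start in both arms, and equal background change. The Month 6 difference is then 10 − 10f: 5 points if the effect builds linearly (f = 0.5), and 0 if it is complete by 3 months (f = 1). At SD 20, sizing on 5 rather than 10 points gives 252 rather than 63 per arm. The Month 3 contrast is 10f, which is the 3-month app effect whatever f is.

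**Where a Month 3 value exists.** The visit table schedules LS7, patient-reported biometrics, the walk test, AF knowledge, AFSS and AFEQT at Month 3. The blood-test row has three marks, read as Initial, Month 6 and Month 12. For lipids and glucose, Initial to Month 6 is therefore the only pre-post pair up to Month 6.

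**The case against.** The plan never names the pairs. A reader might infer that it tests the wait-list arm from the Initial visit and counts app-free months as app effect. The documents do not say either. A Month 3 to Month 6 pair is possible for most outcomes, and aim 2 uses this arm as comparator, not as evidence of app efficacy. The 15-month time point could even hint at a clock started at the wait-list app start, since 3 + 12 = 15, though the visit table stops at Month 12 and the two passages need reconciling. Nor is the advantage of the wait-list design lost: Month 3 and Month 6 values are both scheduled for most outcomes.

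Four further points stand:
- The 9%, 22% and 43% rest on assumed inputs, and the same risk attaches to any uncontrolled pre-post test, including those in the AF CARE arm.
- Re-anchoring at Month 3 does not isolate the app. Referrals are made in both groups at the Month 3 visit, and that column is headed CA, which Purpose defines as catheter ablation.
- One might infer a precision gain from pooling each arm's first 3 months on app (60 rather than 30 participants, SE lower by about 29%). For the reason just given, the two windows are not exchangeable and the gain should not be claimed.
- The future trial's target is fixed at a 10% change, so these data might supply only its SD. However, Research Design expressly says that effect sizes will be used.

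What the objection does not remove is the aim 2 comparison with usual care at 6 months. That is plan text, and at that visit the comparator is on the app.

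**Conclusion.** The point holds in a limited form. The documents establish that the app starts at Month 3 in the wait-list arm, that the only defined baseline is the Initial visit, that both arms share the same test time points, and that aim 2 calls this arm usual care at 6 months. It follows that the Month 6 between-arm difference compares 6 with 3 months of app. On the natural reading of baseline, the wait-list Initial-to-Month 6 change is half usual care by time. Neither is a valid app effect size for the future trial.

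The exposure counts follow from the text alone. All error rates, power values and sample sizes above are illustrations under stated assumptions. Feasibility is the primary aim and efficacy is secondary, so this is a correction that should be made and does not undermine the study.

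**What to change.** In Data Analysis:

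1. Take the effect size for the future trial from the randomized Month 3 between-arm contrast, the only app versus no-app comparison. Use a method for independent groups, since a matched pair test does not fit two separate arms.
2. Label the Month 6 between-arm comparison as immediate versus delayed start (6 versus 3 months on app), and align the wording of aim 2.
3. For wait-list within-group tests of the app period, use Month 3 as the pre-app value for LS7, biometrics, walk test, AF knowledge, AFSS and AFEQT. Report Initial to Month 3 separately as usual-care change.
4. State that lipids and glucose have no scheduled Month 3 value, and so neither a pre-app value at Month 3 nor a Month 3 contrast.
5. Label all within-arm app-period changes descriptive, and claim no precision gain from pooling the two arms' windows.

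This costs analysis wording only, because the visits are already scheduled. The downside is that the effect size then rests on 3 months of app exposure, which should be stated when the multicenter trial is planned.
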